7.3 Medical History

A complete medical history, including a complete review of all current and past diseases will be done on screening visit. Medical history term will be coded using the Medical Dictionary for Regulatory Activities (MedDRA) version 25.0. and summarized by treatment group and overall, by frequency count and percentage of Participants in each system organ class (SOC), preferred term (PT) using Safety Population.

Participants will be counted only once at the preferred term (PT), only once at the system organ class (SOC), and only once at Participant level for the counting of total number of Participants with a medical history term. Counts will be presented in descending frequency unless otherwise specified.

Listings of medical history events for Participants in the Safety Population will be provided.

7.4 **Prior and Concomitant Medications**

Any medication other than study drug, either prescription drug or over the counter (OTC) will be treated as concomitant medication.

Prior Medications

For a Participant in the Safety Population, prior medications will include any medication taken prior to Participant's first dose of Study Medication.

Concomitant Medications

Concomitant medications are defined as prescribed medications and over the counter (OTC) preparations, including herbal preparations and vitamins, other than Study medication taken during the treatment phase.

Prior and concomitant medication will be categorized by preferred Term and anatomical-therapeuticchemical (ATC) classification (highest level available) per World Health Organization Drug Dictionary (WHODRUG B3 March 01, 2022) will be summarized by treatment group and overall, for the Safety Population.

The frequency count and percentage of Participants using each medication will be displayed. Participants who taken the same medication (in terms of PT) more than once will be counted only once for that medication.

Participants taking multiple prior / concomitant medication will be counted only once in summary table. If the Participant is taking medication prior to study drug administration and continues the same drug after study drug administration, then such Participants will be summarized in both prior and concomitant medication summary tables.

All prior and concomitant medications will be presented in a listing for the Safety Population.

7.5 **Protocol Deviation**

Protocol deviations will be identified and classified as minor or major before un-blinding. Protocol deviation categories will be summarized using frequency count and percentage by treatment group.

A listing and summary of protocol deviations will be presented using the Safety Population.

7.6 Study Drug Exposure and Treatment Compliance

A summary table of study drug administration will be provided. Table will be presented using counts and percentages of Number of units administered by treatment groups.

A listing of study drug exposure (administration/dispensation) will be provided.

7.7 Efficacy Analysis

7.7.1 Primary Endpoint

The primary efficacy endpoint is the sum of change in pain intensity from 0 to 8 hours (SPID0-8). The treatment comparisons will be made in the following sequential order for SPID0-8 (each at 0.05 level of significance) in order to protect overall type 1 error at 0.05:

- Naproxen sodium/caffeine 220/65 mg versus Naproxen sodium 220 mg
- Naproxen sodium/caffeine 440/130 mg versus Naproxen sodium 220 mg
- Naproxen sodium/caffeine 220/65 mg versus Naproxen sodium/caffeine 440/130 mg

Once a comparison is statistically non-significant, the subsequent comparisons will be technically ineligible to be declared significant. However, all pairwise comparisons will be presented to provide a complete picture.

The primary efficacy endpoint is the summed pain intensity difference over 0 to 8 hours after Time 0 (SPID0-8). The formula for SPID0-8 calculation is presented in Section 4.1. The primary efficacy endpoint will be analyzed using an analysis of covariance (ANCOVA) model, which will include SPID0-8 as dependent variable, treatment as main effect and baseline pain intensity (Numerical Rating Score) as the covariate.

The least square (LS) mean, standard error (SE) and 95% confidence interval (CI) of LS mean for each treatment group will be reported.

In addition, the least square mean difference, SE, 95% Confidence interval of LS mean difference and p-value for all pairwise treatment group (include placebo) comparisons will be reported. Descriptive statistics (n, mean, SD, median, minimum, and maximum) for SPID0-8 will also be presented by treatment group.

ITT population (without imputation) will be used as the primary analysis for this primary endpoint while PP population (without imputation and single imputation) will be used as secondary analysis to conduct the sensitivity analysis.

In the primary analysis, endpoint will be imputed as described in Section 3.1.1, if any pain assessments are missing or Participant takes rescue medication.

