5.7 General Procedures

In all cases, the reason for withdrawal must be recorded on the screening log and in the participant's medical records.

The participant may object to the generation and processing of post-withdrawal data as specified in Section 10.1.8.

Details for the premature termination of the study as a whole (or components thereof) are provided in Section 10.1.14 (Premature termination of the Study).

Page 28 of 67

6. Study Intervention

Study intervention is defined as any investigational intervention(s), marketed product(s), placebo, or medical device(s) intended to be administered to a study participant according to the study protocol.

The study center will dispense a single-dose (2 tablets) of an assigned treatment within 4.5 hours post-surgery. The tablets and placebo will be administered based on a computer-generated randomization schedule (section 6.1.1) and stratified by the severity of pain experienced (moderate or severe). Moderate participants will use the lowest randomization number available and severe participants will use the highest randomization number available. Participants who characterize their pain severity as mild and have a NRS <5 will not receive treatment and will be discharged from the study site with a prescription for pain medication, if deemed safe, by the Investigator.

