6.1.1 Study intervention assignment

At the beginning of the first treatment period, after completion of the pre-treatment baseline procedures/assessments, participants who meet the entry criteria will be randomized in the study. The randomization will be stratified by baseline pain intensity (moderate vs severe) according to the randomization schedule 3:3:3:1:1 (naproxen sodium/caffeine 220/65 mg; naproxen sodium/caffeine 440/130 mg; naproxen sodium 220 mg; caffeine 100 mg; placebo) prepared prior to the study. Participants will be assigned sequentially to the lowest available number or highest available number (randomization number, RNR) for those with moderate or severe baseline pain intensity, respectively to assure treatment balance between each stratum.

Participants will be numbered according to the following scheme:

Page 30 of 67

Whereas the "Xs" will be replaced with a five digit sequentially assigned number as each participant enters the study (e.g., first participant number will be PPD

The unique participant identifier number will be assigned in numerical order prior to dosing. Participants who characterize their pain severity as *mild* and <5 on the NRS will not receive treatment and be withdrawn from the study.

Once a number has been assigned to a participant, it cannot be reassigned to another participant.

Participants completing the Screening Visit, if not scheduled for surgery the same day, will return to the trial site within 28 days, and if they continue to meet inclusion/exclusion criteria post-surgery will be randomized to one of five treatment groups:

- naproxen sodium/caffeine 220/65 mg (1 tablet plus 1 tablet of placebo)
- naproxen sodium/caffeine 220/65 mg (2 tablets)
- naproxen sodium 220 mg (1 tablet plus 1 tablet of placebo)
- caffeine 100 mg (1 tablet plus 1 tablet of placebo)
- placebo (2 tablets)

Participants will be assigned to treatment groups in accordance with the randomization schedule. The Sponsor will provide a randomization schedule to the study site.

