6.2 Preparation/Handling/Storage/Accountability

All study drugs will be labeled according to the requirements of local law and legislation. Label text will be approved according to the sponsor's agreed procedures, and a copy of the labels will be made available to the study site upon request.

For all study drugs, a system of numbering in accordance with all requirements of Good Manufacturing Practice (GMP) will be used, ensuring that each dose of study drug can be traced back to the respective bulk batch of the ingredients. Lists linking all numbering levels will be maintained by the sponsor's clinical supplies Quality Assurance (QA) group.

A complete record of batch numbers and expiry dates of all investigational products as well as the labels will be maintained in the clinical supply file.

Page 31 of 67

The source of test and reference products will be documented in the clinical supply file.

The investigator or designee must confirm appropriate temperature conditions have been maintained during transit for all study intervention received and any discrepancies are reported and resolved before use of the study intervention. Only participants enrolled in the study may receive study intervention and only authorized site staff may supply or administer study intervention. All study intervention must be stored in a secure, environmentally controlled, and monitored (manual or automated) area in accordance with the labeled storage conditions with access limited to the investigator and authorized site staff. The investigator, institution, or the head of the medical institution (where applicable) is responsible for study intervention accountability, reconciliation, and record maintenance (i.e., receipt, reconciliation, and final disposition records).

The Sponsor will provide sufficient quantity of the study intervention to the study site. The study center will dispense study intervention according to the randomization schedule and stratify randomization by the participant's categorical pain intensity (moderate or severe) post-surgery. Study intervention will be supplied to the study center in multi-dose bottles and dispensed by an unblinded member of the study team.

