9.2 Sample Size Determination

Assuming that the treatment difference between the combo and naproxen alone of 6.5 and common standard deviation of 16.9 with respect to SPID₀₋₈, a total of approximately 528 subjects (144 subjects per active treatment arm and 48 in the caffeine and placebo using a 3:3:3:1:1 ratio) are required to achieve 90% of power with the type I error of 0.05, a total of approximately 556 subjects will be randomized into the study if a drop-out rate of 5% is assumed.

Page 44 of 67

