9.4.1 Efficacy Analyses

For each post-dose time point, Pain Intensity Differences (PID) will be derived by subtracting the pain intensity at the post-dose time point from the baseline intensity score (baseline score – post-baseline score). A positive difference is indicative of improvement. Time-weighted Sum of Pain Intensity Differences (SPIDs) will be calculated for 2, 4, 6, 8, 12, 16, 20 and 24 hours by multiplying the PID score at each post-dose time point by the duration (in hours)

Page 45 of 67

since the preceding time point and then summing these values over 0.5, 1, 1.5, 2, 3, 4, 5, 6, 7, 8, 9, 10, 11, 12, 14, (16, 18, 20 if awake), 22 and 24 hours, respectively.

Similarly, Total Pain Relief Scores (TOTPARs), will be calculated by multiplying the pain relief score at each post-dose time point by the duration (in hours) since the preceding time point and then summing these values.

In all analyses for participants who take rescue medication, all pain intensity scores after intake of rescue medication will be imputed by the worse of the baseline or the score assessed immediately before taking rescue medication. All pain relief after intake of rescue medication will be imputed by "no relief" (0).

Endpoint	Statistical Analysis Methods
Primary	The primary efficacy analyses population will be based on the ITT population.
	Sum of Pain Intensity Difference over 8 hours: SPID ₀₋₈ be analyzed using an analysis of covariance model (ANCOVA) with treatment as fixed effect and baseline pain intensity score as the covariate. A 95% of confidence interval (CI) for the treatment differences and pairwise p-values will be calculated based on the above mentioned model.
Secondary	Total Pain Relief over 8 hours: TOTPAR ₀₋₈ will be analyzed similarly as for the primary endpoint.
	Time to first use of rescue medication. If a participant did not take the rescue medication during the treatment period, (s)he will be censored at the time of last assessment. Time to first use of rescue medication will be estimated and plotted using Kaplan-Meier method and analyzed using log-rank test.

Page 46 of 67

Secondary

The SPID0-2, 0-4, 0-6, 6-12, 0-12, 12-16, 16-20, 12-24, 16-24 and 0-24 will be analyzed using the same methodology as for SPID₀₋₈.

TOTPAR0-2, 0-4, 0-6, 6-12, 0-8, 0-12, 12-16, 16-20, 12-24, 16-24 and 0-24 will be analyzed using the same methodology as for SPID₀₋₈.

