Pain Intensity Difference (PID) and Pain Relief scores at 0.5, 1, 1.5, 2, 3, 4, 5, 6, 7, 8, 9, 10, 11, 12, 14, (16, 18, 20 if awake), 22 and 24 hours post-dose. Descriptive statistics for each time point and graphical illustrations of the time effect curves will be presented.

Time to first perceptible relief measured by a stopwatch, time to meaningful relief measured by a stopwatch, and time to first perceptible relief confirmed by meaningful relief defined as the time to perceptible pain relief (the first stopwatch time) for those participants who had meaningful pain relief (the second stopwatch time) will be analyzed similarly as for the time to first use of rescue medication.

Time to achieve complete pain relief will be analyzed similarly as for the time to first use of rescue medication.

The cumulative proportion of participants taking rescue medication over time will be analyzed using Chi-square tests and curves over time will be plotted. Frequency tables will be tabulated for the number of times that the participant took rescue medication over the 24 hour period.

Peak PID and peak pain relief will be analyzed descriptively.

Cumulative percent of participants with 'at least a 2-point PID' and cumulative percent of participants achieving complete pain relief will be plotted over time and will be analyzed using Chi-square tests.

Global Assessment of the investigational product will be analyzed using CMH method with modified ridit score.

Page 47 of 67

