10.1 Appendix 1: Regulatory, Ethical, and Study Oversight Considerations

10.1.1 Regulatory and Ethical Considerations

- This study will be conducted in accordance with the protocol and with the following:
 - Consensus ethical principles derived from international guidelines including the Declaration of Helsinki and Council for International Organizations of Medical Sciences (CIOMS) International Ethical Guidelines
 - o Applicable ICH Good Clinical Practice (GCP) Guidelines
 - o Applicable laws and regulations

The protocol, protocol amendments, ICF, Investigator Brochure, and other relevant documents (e.g., advertisements) must be submitted to an IRB/IEC by the investigator and reviewed and approved by the IRB/IEC before the study is initiated. Any amendments to the protocol will require IRB/IEC approval before implementation of changes made to the study design, except for changes necessary to eliminate an immediate hazard to study participants.

The investigator will be responsible for the following:

- Providing written summaries of the status of the study to the IRB/IEC annually
 or more frequently in accordance with the requirements, policies, and
 procedures established by the IRB/IEC
- Notifying the IRB/IEC of SAEs or other significant safety findings as required by IRB/IEC procedures

Page 48 of 67

• Providing oversight of the conduct of the study at the site and adherence to requirements of 21 CFR, ICH guidelines, the IRB/IEC, European regulation 536/2014 for clinical studies (if applicable), and all other applicable local regulations

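### The primary SPID0-8 ANCOVA and the SAP's other SPID, TOTPAR and peak-score ANCOVAs omit the moderate/severe randomisation stratum without a stated reason; adding it costs almost nothing and gains little

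*SAP*

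**What the plan says.** Protocol 6.1.1 sets the design: "The randomization will be stratified by baseline pain intensity (moderate vs severe) according to the randomization schedule 3:3:3:1:1". Participants with moderate pain take the lowest available randomisation number and those with severe pain the highest, with the aim of balancing treatments within strata. Protocol 6 says the same, and Protocol 6.2 has the site "stratify randomization by the participant's categorical pain intensity (moderate or severe) post-surgery".

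The analysis models do not carry this factor:

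- **Primary, SPID0-8:** Protocol 9.4.1 has "treatment as fixed effect and baseline pain intensity score as the covariate". SAP 7.7.1 makes the covariate explicit: "treatment as main effect and baseline pain intensity (Numerical Rating Score) as the covariate".
- **Other SPID and TOTPAR intervals:** SAP 7.7.2 uses the primary method for SPID and the same two terms for TOTPAR.
- **Peak PID and Peak Pain Relief:** SAP 7.7.2 uses the same two terms. These models exist only in the SAP, since Protocol 9.4.1 says "Peak PID and peak pain relief will be analyzed descriptively".

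The category is used elsewhere. SAP 7.7.2 stratifies every log-rank test by categorical baseline pain. Neither document explains its absence from the ANCOVAs, and SAP 7.13 declares no changes from the protocol.

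**The concern.** When allocation is restricted on a factor, the analysis would normally include that factor. Stratified allocation balances the arms on it and so already lowers the true sampling variance of the treatment difference. A model without the factor leaves its variation in the residual, so the reported standard error is, if anything, slightly too large.

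The stake is precision only: slightly wide confidence intervals and a slightly conservative test. The first comparison (one FDC tablet against naproxen sodium 220 mg) gates the rest of the sequence in Protocol 9.1, so precision there has some value.

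Using the category in the log-rank tests and not in the ANCOVAs is not in itself an inconsistency. A stratified log-rank test needs discrete strata, while an ANCOVA can use the NRS.

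**Working it through.** **Inputs from the documents** (Protocol 9.2, repeated in SAP 2.3): difference 6.5; "common standard deviation of 16.9"; 144 per active arm and 48 in each of the caffeine and placebo arms; 90% power; alpha 0.05, taken as two-sided because the plan reports 95% CIs.

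**The plan's own figure.** n per arm = 2 × [16.9 × (1.960 + 1.282) / 6.5]² = 142.06, so 143. The plan's 144 fits the 3:3:3:1:1 ratio. The total is 3 × 144 + 2 × 48 = 528, and 528 / 0.95 gives 556 randomised. Power at 144 per arm is 0.904 (normal approximation). The sample size reproduces and needs no change.

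**Degrees of freedom.** Residual df = 528 − 5 arms − 1 NRS slope = 522. With the two-level stratum it is 521.

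**Assumptions that the documents do not supply.** R² is the partial R² of the category given NRS, taken from 0 to 0.05. The 16.9 is read as the SD after NRS adjustment.

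**Formulas.** SE = 16.9 × √(1 − R²) × √(2/144); half-width = t(0.975, df) × SE; power = Φ(6.5/SE − 1.96).

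| Partial R² | SE | 95% CI half-width | Power |
|---|---|---|---|
| 0 | 1.992 | 3.91 | 90.4% |
| 0.01 | 1.982 | 3.89 | 90.7% |
| 0.03 | 1.962 | 3.85 | 91.2% |
| 0.05 | 1.941 | 3.81 | 91.8% |

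Noncentral-t power is about 0.1 point lower in each row (90.3%, 90.6%, 91.1%, 91.7%).

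**What the term costs if the category is uninformative.** This was simulated with arms of 144/144/144/48/48 and 1,500 trials per case. The assumed inputs were 40% severe, NRS 5–10 correlated with category, and one list in blocks of 11, with moderate participants drawing from the bottom and severe from the top. The mean ratio of the SE with the factor to the SE without it was:

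| Partial R² | Lowest/highest-number allocation | Allocation ignoring strata |
|---|---|---|
| 0 | 1.0003 | 1.0009 |
| 0.01 | 0.9953 | 0.9959 |
| 0.05 | 0.9748 | 0.9756 |

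The last column is shown because SAP 2.4 describes ascending-order assignment without mentioning strata. The ratios agree with √(1 − R²), which is 0.995 at 0.01 and 0.975 at 0.05.

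**Bias and type I error.** A second simulation used blocks of 11 within stratum and 4,000 runs per setting. It assumed an NRS–category correlation of about 0.47, an NRS slope of 2, and a residual SD of 16.9 after both terms. Each pair of figures is without / with the stratum.

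| Category effect (SPID units) | Type I error | Power |
|---|---|---|
| 0 | 0.052 / 0.053 | 0.901 / 0.900 |
| 4 | 0.048 / 0.049 | 0.899 / 0.901 |
| 8 | 0.046 / 0.048 | 0.899 / 0.906 |
| 12 | 0.043 / 0.052 | 0.888 / 0.909 |

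The treatment estimates were practically identical under both models. The Monte Carlo standard error of a 0.05 rejection rate is √(0.05 × 0.95 / 4,000) = 0.0034. The type I figures therefore show no inflation, and slight conservatism without the term when the category effect is large.

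**The case against.** The strongest reply is that this is a modelling preference and not an error. The protocol and SAP agree on the primary model, nothing in them requires the stratum in the ANCOVA, and the planned power stands. The stratum and the covariate are two pre-dose ratings of the same pain, and the model keeps the finer scale. **This stands as far as it goes**, and it is why the point is minor. It does not make the category redundant. NRS enters as one linear term over a range cut off below 5 by inclusion criterion 8, so the category may still add something.

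Second, the upper part of the R² range is generous. With 40% severe and a correlation of 0.47, the category variance given NRS is 0.24 × (1 − 0.47²) = 0.187. An R² of 0.03 then needs a category effect of √(0.03 × 16.9² / 0.187) ≈ 6.8 SPID units at fixed NRS, and 0.05 needs about 8.7. Both exceed the 6.5-unit treatment effect. **This stands**, given those assumed inputs.

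Third, the closed form somewhat overstates the power gain, because stratified allocation has already removed most of the stratum variance from the estimate itself. A 6,000-trial simulation of the lowest/highest-number allocation with the same inputs and R² of 0.05 gave a true SD of the estimate of 1.963 without the factor and 1.952 with it. Power was 90.7% against 91.7%, a gain of 1.0 point where the closed form implies 1.4. **This stands**: most of the effect is on the reported standard error and interval.

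Finally, changing the SAP alone makes the primary model differ from Protocol 9.4.1. **True**, but a declared change in SAP 7.13 deals with it.

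**Conclusion.** The concern holds, at minor severity. It is certain from the text that the randomisation factor is missing from all the SPID, TOTPAR and peak-score ANCOVAs and that no reason is given.

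The consequence is small and cannot be fixed from the documents, which give neither the moderate/severe split, nor the NRS–category correlation, nor the category's effect on SPID0-8. Under the stated assumptions the reported standard error is at most about 2.5% larger than it need be (R² of 0.05), and the power gain is about 1 point or less when the balance from stratified allocation is counted. There is no bias, no type I error inflation and no threat to the sample size. The case for the change is that its cost is close to zero even if the category turns out to be uninformative.

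**What to change.** Before unblinding, add the moderate/severe category as randomised to the primary SPID0-8, other SPID, TOTPAR, Peak PID and Peak Pain Relief ANCOVAs in SAP 7.7.1, 7.7.2 and 7.7.3, alongside treatment and baseline NRS. Record it in SAP 7.13 as a change from the Protocol 9.4.1 model, or align 9.4.1 for SPID and TOTPAR at the next amendment. Protocol 9.4.1 has no peak-score ANCOVA to edit. While SAP 7.7.2 is open, state that the CMH strata for the Global Assessment are the same two categories; this is a clarification and does not bear on the point above.

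The cost is one model term, one residual degree of freedom (522 to 521 at n = 528) and text edits in four SAP sections. The data are already collected before dosing. Aligning the protocol costs more, because "Any amendments to the protocol will require IRB/IEC approval before implementation" (Protocol 10.1.1). The documents do not show whether the blind has been broken. If it has, the model with the stratum should be reported only as a labelled supplementary analysis.
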